12.1 Severity

Severity of the adverse event will be defined as follows:

Mild – Discomfort noticed but no disruption of normal daily activity
Moderate – Discomfort sufficient to reduce or affect daily activity
Severe – Inability to work or perform normal daily activity
Life Threatening – Represents an immediate threat to life.

12.2 Determination of Relationship of Adverse Event to FMT

There will be four categories of possible relationship between the adverse event and FMT. Determination of drug-relatedness of the adverse event to FMT will be determined by the investigator.

Category 1: Probable (must have first three)

A probable relationship will be assigned to an adverse event that is considered, with a high degree of certainty, to be related to FMT. An adverse event may be considered probable if:

1. It follows a reasonable temporal sequence from administration of the FMT.
2. It cannot be reasonably explained by the known characteristics of the subject's clinical state, environmental or toxic factors, or other modes of therapy administered to the subject.
4. It follows a known pattern of response to FMT

Category 2: Possible (must have first two)

A possible relationship will be assigned to an adverse event when the connection with FMT administration appears unlikely but cannot be ruled out with certainty. An adverse event will be considered possible if:

1. It follows a reasonable temporal sequence from administration of FMT
2. It may have been produced by the subject's clinical state, environmental or toxic factors, or other modes of therapy administered to the subject
3. It follows a known pattern of response to FMT

Category 3: Remote (must have first two)

FMT in UC-associated Pouchitis

Version 3.0, date finalized 06/26/2017

An adverse event will be considered remote if:

1. It does not follow a reasonable temporal sequence from administration of FMT
2. It may readily have been produced by the subject's clinical state, environmental or toxic factors, or other modes of therapy administered to the subject.
3. It does not follow a known pattern of response to FMT

Category 4: Unrelated

An adverse event will be considered unrelated if it is judged to be clearly and incontrovertibly due only to extraneous causes such as disease, environment, etc. while not meeting the criteria for drug relationship as listed above for remote, possible, or probable.

12.3 Serious Adverse Event

A serious adverse event is any experience that suggests a significant hazard, contraindication, side effect or precaution and meets at least one of the following criteria:

- Is fatal (results in death);
- Is life-threatening;
- Requires in-patient hospitalization or prolongs existing hospitalization;
- Results in persistent or significant disability/incapacity;
- Results in a congenital anomaly/birth defect;
- Is medically significant or requires intervention to prevent one or other of the outcomes listed above.

The clinical judgment of the investigator shall be used in deciding whether a certain situation may warrant consideration as a serious adverse event but may not meet the above criteria. This medical event may not be immediately life-threatening or result in death or hospitalization but may jeopardize the subject or may require intervention to prevent one of the outcomes listed in the definitions above.

12.4 Reporting of Serious Adverse Events

All adverse events considered serious and unexpected shall be reported to

- FDA (via form MedWatch 3500-see Appendix 3) within 10 calendar days (by fax)
- Emory University IRB within 10 business days
- DSMB within 7 days

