7. PATIENT SAFETY

The risks of this study are limited to those inherent with mucosal tissue biopsy and fecal microbial transplant with use of a flexible sigmoidoscopy.

The primary risk associated with a mucosal tissue biopsy is bleeding from the area of biopsy. Significant bleeding from the biopsy site is uncommon, but possible (1 in 1,000). Even more rarely (1 in 3,000), a perforation can be made at the site of biopsy which would require surgery to repair. To minimize these risks, standard practice is to not take a biopsy of large vessel, not to repair.

To minimize these risks, standard practice is to not take a biopsy of large vessel, not more than one biopsy from a given mucosal site and not to over distend the bowel lumen while taking biopsies. Furthermore, mucosal biopsies are not painful as the bowel lining does not have pain fibers to sense pain. In addition, all the above mentioned risks apply regardless if the biopsy is done for donating tissue to this study or for diagnostic purposes. Mucosal biopsy sampling will be performed by medical staff with expertise in performing these procedures.

Research associated peripheral blood draws may result in some discomfort or risk of bruising at the site of the needle entry. There is a remote risk of fainting from a vasovagal response or local infection. These risks will be minimized using trained phlebotomists and aseptic technique. Sample collections will be performed with the patient seated or recumbent.

There is not significant risk to urine donation. There is not significant risk to stool donation.

The primary risks of fecal microbiota transplantation are transmission of infection and potential immune stimulation. We will be using a standard donor who will be screened for transmittable infections through serologic and stool testing. In addition, the donor will be screened clinically for illness in which there is potential for disruption of normal gastrointestinal flora such as irritable bowel syndrome. The donor will be excluded from the study if he is found to have such an illness. The risk associated with placement of the transplant enema through flexible sigmoidoscopy is discomfort. Small volume (100 mL-200mL) enemas will be used to minimize this risk.

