11. DATA SAFETY MONITORING PLAN

A committee consisting of two physicians, [name] (Assistant Professor, Division of Infectious Diseases) and [name] MD, (Assistant Professor, Division of Pulmonary and Critical Care) has been created. [name] and [name] have agreed to be part of the committee and will not have any direct participation or interests in the study. The committee will meet emergently in the event of the reported SAE and consider the future course based on the outcome of the event. If no SAE is reported, the committee will meet every 6 months to assess the safety and review the AEs.

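### Section 12.4 sends the safety committee only serious and unexpected events, although section 11 has it meet on any reported SAE, so a serious event classed as expected has no required route or deadline before the next 6-monthly meeting

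*Combined protocol and SAP*

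**What the plan says.** Section 11 (Data Safety Monitoring Plan) gives the two-physician committee two modes of working. The emergency mode is: "The committee will meet emergently in the event of the reported SAE and consider the future course based on the outcome of the event". The routine mode is: "If no SAE is reported, the committee will meet every 6 months to assess the safety and review the AEs". Neither sentence makes expectedness a condition.

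Section 12.4 is the one place that says which individual events must be sent, to whom and by when. Its lead-in is "All adverse events considered serious and unexpected shall be reported to". Three recipients follow: the FDA (10 calendar days), the Emory IRB (10 business days) and, last, "DSMB within 7 days". The lead-in applies to all three.

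Section 12.3 defines an SAE as "any experience that suggests a significant hazard, contraindication, side effect or precaution and meets at least one of the following criteria". The listed criteria concern outcome and medical significance; none refers to expectedness.

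Section 7 sets out what the protocol already foresees. For the transplant: "The primary risks of fecal microbiota transplantation are transmission of infection and potential immune stimulation". For the biopsy it gives significant bleeding at 1 in 1,000 and adds: "Even more rarely (1 in 3,000), a perforation can be made at the site of biopsy".

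Section 12 limits adverse event collection to events related to study procedures.

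**The concern.** The emergency meeting depends on a report being made, and section 12.4 obliges a report for only part of what section 12.3 calls serious. The part left out is serious events judged expected. Those are most naturally the kinds the protocol names in advance. Section 12.2 points the same way: fitting a recognised pattern of FMT response counts towards a probable relationship, so an event that looks clearly caused by FMT may also be the easier one to call expected.

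Safety and tolerability are the primary objective (section 3.1), and the section 11 committee is the only body set up specifically to watch them. Recipients receive screened standard-donor stool, so a serious infection in one recipient may bear on those treated next. If the committee is not told, further patients can be treated before it has looked at the event.

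**Working it through.** The plan states no figure for this point, so there is none to reproduce. The check is a comparison of the text, followed by simple accrual arithmetic.

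**1. The rules side by side**

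| Question | Section 11 | Section 12.4 |
|---|---|---|
| Which event? | Any reported SAE | Serious and unexpected only |
| What follows? | Emergency meeting | Report to FDA, IRB and DSMB |
| Time limit | None for the report; 6-monthly meetings if there is no SAE | 7 days for the DSMB |
| Expectedness defined? | Not mentioned | Used, but not defined; no reference document named |

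**2. Following one event through**

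Take a recipient hospitalised with an infection that may have come from the donor stool.
- Under 12.3, hospitalisation is a listed seriousness criterion.
- If the event is judged unexpected, 12.4 requires a report to the DSMB within 7 days and section 11 then calls the emergency meeting.
- If it is judged expected, because section 7 lists infection transmission as a risk, 12.4 requires no report to any of the three recipients. No other section supplies a route or deadline. The next certain review is the routine meeting.

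The longest wait is then about 6 × 30.44 = 183 days against 7 days, a ratio of 183/7 ≈ 26.

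**3. Patients treated in the meantime**

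Inputs: N = 11 (section 6); accrual over 12 months (section 6) or 24 months (timeline in section 3.6 b); meeting interval 6 months (section 11); reporting limit 7 days (section 12.4). Assumptions: even accrual, and treatment continuing unchanged.

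Formula: patients treated = (N / accrual months) × months of delay.

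| Delay | 12-month accrual | 24-month accrual |
|---|---|---|
| Full 6 months (maximum) | 11/12 × 6 = 5.5 | 11/24 × 6 = 2.75 |
| 3 months (mean, if the event falls at random in the interval) | 11/12 × 3 = 2.75 | 11/24 × 3 ≈ 1.4 |
| 7 days | 11/12 × 7/30.44 ≈ 0.21 | 11/24 × 7/30.44 ≈ 0.11 |

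The maximum is 5.5/11 = 50% or 2.75/11 = 25% of the sample.

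**4. How likely the case is**

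If the section 7 biopsy rates are taken per patient, the expected counts are 11 × 1/1,000 = 0.011 bleeds and 11 × 1/3,000 ≈ 0.004 perforations. The protocol gives no rate for transmitted infection or immune stimulation. The point is therefore about what happens if such an event occurs, not about its being likely.

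**The case against.** The strongest reply is that section 12.4 says what must be reported within set limits and does not say that other SAEs are kept from the committee. Section 11 speaks of a reported SAE without qualification and keeps the 6-monthly schedule for when there is none, so it seems to presuppose that all SAEs arrive. That reading is fair and may be what was intended. But no section sets up that reporting, and the section headed as the SAE reporting rule contradicts it. The two still have to be reconciled.

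Second, calling a transmitted infection expected is an inference. Section 3.6 a requires negative donor results before use, so an investigator could reasonably call such an infection unexpected. This stands: the plan permits the expected classification but does not require it.

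Third, section 13.1 commits the study to GCP, ICH guidelines and regulatory requirements. That is a general statement and sets no route or deadline to this committee.

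A reader might also infer more than the text supports:
- *Transmitted infection is the top-ranked risk.* Section 7 names it jointly with immune stimulation and ranks neither.
- *All recipients share one donor.* Section 7 speaks of a single standard donor, but section 3.6 a uses the plural.
- *The committee is the only independent check.* The FDA and IRB also receive reports, though under the same filter.
- *5.5 patients is the expected exposure.* It is a maximum, reached only if the event falls just after a meeting.
- *Section 12.3 removes deaths or hospitalisations put down to underlying disease.* The definition does join a hazard clause to the seriousness criteria, but it does not mention attribution, and its closing paragraph leaves room for investigator judgement. That exclusion is one possible reading, so clarification is enough.

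**Conclusion.** The concern holds as an inconsistency between two stated rules, not merely a missing detail. Followed as written, section 12.4 allows a serious event classed as expected to reach the committee only at its routine meeting, although section 11 intends an emergency review of a reported SAE. The documents do not show that such events would be withheld in practice, or that an infection would in fact be classed as expected.

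The possible cost is treatment of up to a quarter to a half of the sample before the committee reviews the event, and about half that on average; prompt reporting would hold it to a fraction of one patient. This rests on even accrual over 12 or 24 months, on treatment continuing in the meantime (the documents do not say what the investigator would do), and on the section 11 committee and the section 12.4 DSMB being the same body, which the text never states.

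**What to change.** 1. **Section 12.4.** Separate the DSMB line from the other two, for example: *All SAEs, whether expected or unexpected, are reported within 7 days to the DSMB, which is the committee described in section 11.* Keep the serious-and-unexpected filter for the FDA and IRB lines, and define unexpected against a named reference document.
2. **Section 12.** Provide that SAEs are collected regardless of relationship. Under the present limit to procedure-related events, some SAEs might never be recorded and so could not be reported.
3. **Section 12.3.** State that meeting any one of the listed seriousness criteria is sufficient for an event to be an SAE.

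Section 11 can then stay as it is. The cost is a few sentences of protocol wording and, with 11 patients, possibly a few extra SAE reports and committee meetings. No endpoint, sample size or analysis changes.

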3. STUDY DESIGN

The primary investigative design will be a single arm study to determine if FMT has the potential to be used in the treatment of chronic pouchitis.

3.1 *Study Objectives:*

Primary Objective: To determine the safety and tolerability of fecal microbiota transplant (FMT) in treatment of chronic pouchitis

Secondary Objective: To study the microbial environment of IPAA/UC associated pouches in patients presenting with symptoms of pouchitis with and without endoscopy-visualized pouchitis and to assess the impact of the therapy on the patient's perceived quality of life

3.2 *Study design Type/Phase:* This is a two center, Phase 1 open label study designed to determine the safety, tolerability and use of fecal transplant in patients with pouchitis and to study the differences in microbiome in patients before and after treatment with FMT.

3.3 *Sites Centers of Research:* This study will be conducted in the Emory Clinic- Adult Digestive Disease Clinic and Colorectal Surgery Clinic, the Emory Center Endoscopy Center, and St. Joseph's Hospital (SJH) in Atlanta, GA.

3.4 *Measures to minimize/avoid bias:* Eligible subjects will be given options of other treatments if they choose not to participate.

3.5 *Study duration:* The total duration of the study for each patient will be twelve weeks.

3.6 *Study Procedures*

The following protocol essentially requires two sets of study procedures. One set of study procedures outlines testing requirements for the donor of allogenic human feces (see **Table 1.** Donor Related Study Activities). The other set outlines activities and expectations of the research participant who will receive the donated stool specimen (see **Table 2.** Research Participant Study Activities). The donor set of activities will be managed by [name], a sub-investigator and Associate Professor of Medicine within the Division of Infectious Diseases. In the past, [name] has overseen the donor recruitment and screening within previous FMT trials via ordering the appropriate antibody screens, fecal sample preparation (e.g. use of saline, etc.) and any other necessary tests to ensure that the fecal specimen is non-infectious and safe for insertion into research participants. [name] still oversees this process and prepares the allogenic human fecal FMT in UC-associated Pouchitis

Version 3.0, date finalized 06/26/2017

donation in her lab on site. However, she will not be able to provide these activities listed in **Table 1** for effort.

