⁴ Screening labs for hemoglobin (Hgb), platelet count, and absolute neutrophil count (ANC) may be performed within six months of screening visit

3.6. a) Donor Stool Collection and Processing

The standard donor stool will be obtained from a donor who has undergone testing for potential transmittable infections. These include Hepatitis A, Hepatitis B, Hepatitis C, syphilis, HIV, *H pylori*, *Salmonella*, *Shigella*, *Campylobacter*, *C. difficile*, as well as screening for ova and parasites, and multidrug resistant organisms (specifically carbapenemase-producing *Enterobacteriaceae* and vancomycin-resistant *Enterococcus*). This testing is performed through Emory Medical Laboratories. In addition, the donor will be screened for illnesses that would exclude him from donating stool for the current study (see attached screening questionnaire). Donor screening will be completed and all results confirmed negative prior to use of donor stool for transplant. Standard donors will be re-screened every six months.

The standard donor voids the stool at home just prior to leaving for work in the morning. The stool is dropped off in the microbiology laboratory within 60 minutes of being voided. The stool is processed within 60 minutes of the drop off, and administered within 120 minutes of the processing. The time that elapses from the stool being voided by the donor and administered to the patient ranges from 60-240 minutes. Donor stool will be handled as a level 2 biohazard with appropriate universal precautions.

Appropriate Personal Protective Equipment (PPE) will be worn by personnel while handling/processing donor fecal material:

- Nitrile gloves will be worn while working with all potentially infectious agents. Gloves should be removed before touching common objects in public areas. Hand washing will be performed each time gloves are changed.
- Gloves should be removed prior to removal of other PPE. Gloves should be removed before leaving the laboratory.
- Lab coats will be worn over clothing while handling/processing stool specimen and preparing FMT solution

FMT in UC-associated Pouchitis

Version 3.0, date finalized 06/26/2017

- Contaminated clothing will be decontaminated and laundered on-site or by a commercial laundry service.
- Protective eyewear/goggles will be used, if splash potential exists
- Laboratory access will be limited to authorized personnel only.

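### The 7-day duty to report to the DSMB covers only serious events that are also unexpected, so a serious event classed as expected could wait for the 6-monthly meeting

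*Combined protocol and SAP*

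**What the plan says.** Three sections of the combined protocol and SAP bear on this.

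- **Section 12.4** opens its list of recipients with "All adverse events considered serious and unexpected shall be reported to". Three follow: the FDA (10 calendar days), the Emory IRB (10 business days) and the DSMB (7 days).
- **Section 12.3** says: "A serious adverse event is any experience that suggests a significant hazard, contraindication, side effect or precaution and meets at least one" of a list of seriousness criteria. Expectedness is not among them.
- **Section 11** sets the committee's meetings. "The committee will meet emergently in the event of the reported SAE and consider the future course based on the outcome of the event". Otherwise: "If no SAE is reported, the committee will meet every 6 months to assess the safety and review the AEs".

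Section 7 lists the known risks. For biopsy these are significant bleeding (1 in 1,000) and perforation requiring surgery (1 in 3,000). For the transplant, "The primary risks of fecal microbiota transplantation are transmission of infection and potential immune stimulation", with no rate given. Section 12 limits collection to adverse events related to study procedures.

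This point takes the committee of section 11 and the DSMB of section 12.4 to be the same body.

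**The concern.** The emergency meeting depends on a report, and the only rule that requires a report to the committee carries a condition that the meeting rule does not. Section 12.2 gives the investigator the judgment on relatedness, but no section says who judges expectedness or against what list. A complication already named in section 7 could reasonably be called expected. Nobody would then be obliged to tell the committee before its routine meeting.

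The primary objective in section 3.1 is "To determine the safety and tolerability of fecal microbiota transplant (FMT) in treatment of chronic pouchitis". The committee's task after an SAE is to consider how the study should go on, and it cannot do that for an event it has not been told about. At stake is a delay in independent review while further subjects are treated. The event would not be concealed, since the 6-monthly meeting would see it.

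**Working it through.** **1. Is there another route to the committee?** Comparing the sections:

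| Section | Trigger | Duty to report | Deadline |
|---|---|---|---|
| 12.4 | serious and unexpected | yes | 7 days to DSMB |
| 11 | a reported SAE | none stated | none stated |
| 12.3 | defines an SAE by seriousness | none | none |
| 13.1 | general compliance with GCP, ICH and regulations | none specific to the committee | none stated |

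No section requires prompt reporting of a serious but expected event to the committee.

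**2. How many subjects could be treated during the wait?** The plan gives no figure to reproduce. Inputs: 11 patients over 12 months (section 6); a 24-month period for all aims and enrolment (Timeline, section 3.6 b); meetings every 6 months (section 11). Assumptions: even accrual, meetings counted from month 0, an SAE soon after treatment, and dosing unchanged until the committee meets.

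Treatment time of subject i + 1 is (i + 0.5) × T/11 months, for i = 0 to 10. For each subject in turn as the index case, count the later subjects treated before the next meeting.

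- T = 12 (spacing 12/11 = 1.09 months), meetings at 6 and 12: 4, 3, 2, 1, 0, 5, 4, 3, 2, 1, 0. Sum 25, mean 25/11 = 2.27, range 0 to 5.
- T = 24 (spacing 24/11 = 2.18 months), meetings at 6, 12, 18 and 24: 2, 1, 0, 1, 0, 2, 1, 0, 2, 1, 0. Sum 10, mean 10/11 = 0.91, range 0 to 2.

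Subject 6 falls exactly on a meeting date in both cases. Counting that subject before the meeting instead leaves both sums unchanged.

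Sensitivity: shift the meeting dates across a full 6-month cycle and let the SAE begin 0, 14 or 28 days after treatment.

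| Accrual | Mean further subjects | Maximum |
|---|---|---|
| 12 months | 1.45 to 2.82 | 4 to 6 |
| 24 months | 0.73 to 1.36 | 2 to 3 |

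For comparison, subjects treated during a 7-day reporting window: 11 × 7/365.25 = 0.21 under 12-month accrual, and half that, 0.11, under 24-month accrual. The protocol does not say how soon after a report the committee convenes.

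**3. How likely is a listed biopsy complication?** Section 7 gives 1/1,000 for significant bleeding and 1/3,000 for perforation, without stating the unit. Treating the two as independent, the chance of at least one in k exposures is 1 − [(1 − 1/1,000)(1 − 1/3,000)]^k.

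- Per procedure, k = 11: 1.5%.
- Per biopsy at the maximum of 6 each (sections 3.7 and 4), k = 66: 8.4%.

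A significant bleed need not meet the criteria of section 12.3, so for biopsy SAEs these figures lean high. No comparable figure can be given for a donor-derived infection.

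**The case against.** The strongest reply is that section 11 already points the right way. It reserves the 6-monthly schedule for the case in which no SAE is reported, and section 12.3 counts expected events as SAEs. Read together, the routine meeting is the no-SAE default and not a channel for expected SAEs. This stands as evidence of intent, and section 12.4 does not itself say that only unexpected events go to the DSMB. But section 11 names no reporter and no deadline, and the section that does is narrower. Section 13.1's general commitment to GCP and regulations does not supply a committee deadline either, and what those outside sources require cannot be checked here.

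A reader might infer that the protocol deliberately exempts expected SAEs, or that a donor-derived infection would go unreported while the next recipients are exposed. The documents do not support either. Section 3.6 a) states: "Donor screening will be completed and all results confirmed negative prior to use of donor stool for transplant". An infection transmitted despite negative screening could well be called unexpected, which would bring it under the 7-day rule. Stool also arrives with a questionnaire on recent illness and antibiotics, and is given fresh: "The time that elapses from the stool being voided by the donor and administered to the patient ranges from 60-240 minutes". The text describes no stored batch that recipients would share. Donors are re-screened as well, every four weeks according to section 3.6 and Table 1, or every six months according to section 3.6 a). These safeguards lower the infection risk, but they do not inform the committee.

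The events most naturally classed as expected are biopsy complications. Section 7 notes that those risks apply whether the biopsy is for research or diagnosis, so they say less about FMT or the next recipient. It is also fair that the investigators would know of the event and might pause dosing themselves. The counts above assume that they do not.

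**Conclusion.** The mismatch is real and worth correcting, at modest weight. An SAE classed as expected has no prompt reporting duty to the committee, although section 11 appears to intend that every SAE gets there. If one waited and dosing continued, a mean of 2.3 further subjects (range 0 to 5) would be treated first under section 6's 12-month accrual, or 0.9 (range 0 to 2) if accrual filled 24 months. Varying meeting dates and onset gives means of 1.5 to 2.8 and 0.7 to 1.4.

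These numbers are conditional on a serious event, classed as expected, not passed on under section 11, and followed by unchanged dosing. The first condition alone is improbable for biopsy complications (about 1.5% to 8%, depending on the unit of section 7's rates) and unquantified for infection. The headline should not be read as five recipients exposed to an infected donor: that takes the maximum under faster accrual and applies it to the event least clearly covered by the gap. What the text supports is an ambiguous safety trigger in a Phase 1 safety study that can be cheaply removed.

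**What to change.** Make two edits in one amendment.

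- **Section 12.4:** take the DSMB out of the shared list and give it its own line: *All serious adverse events, expected or unexpected, are reported to the safety committee (DSMB) within 7 days.* Leave the FDA and IRB lines unchanged.
- **Section 11:** make the emergency-meeting trigger *any SAE, expected or unexpected*.

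Section 7 should not become the list of expected events. If the sponsor later defines unexpected for the FDA and IRB lines, it should state that a suspected donor-derived infection always counts as unexpected.

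No new body or data collection is needed, since the change stays within the procedure-related events section 12 already collects. The cost is that the existing two-physician committee may occasionally meet for an expected procedural event such as a biopsy bleed.
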